^j Intense PK collection will be performed **at select sites** in up to approximately 30 subjects at time points described for Group A. Sparse PK collection will be performed in the remaining subjects at time points described for Group B. Pharmacokinetic blood samples should be collected at the exact nominal time point as noted above (see hour postdose column). If unable to collect a blood sample at the specified nominal time point, collect it as close as possible to the nominal time point and record the actual collection time. Pharmacokinetic samples not collected at exact nominal time point will not be considered protocol deviations. Pharmacokinetic samples collected in cycle 7 and beyond should be performed prior to AMG 510 dosing.

^k **Tumor markers will be performed as per standard of care and reported on the applicable eCRF.**

^l Plasma ctDNA is to be collected predose as indicated in the **Schedule of Assessments**, and at response.

^m **Cell pellet will be used for pharmacogenetics analysis in subjects who consent.**

ⁿ Stool sample **collected predose (-3 days) and at EOT.**

^o Subjects will provide archived FFPE samples (collected within 5 years) for *KRAS p.G12C* mutation confirmation or undergo tumor biopsy that enables *KRAS p.G12C* testing prior to starting all other screening procedures. .

Approved

-
- ^p After enrollment, optional tumor biopsy will be performed for subjects who consent to this assessment. It will be performed, if feasible, on cycle 1 day 8 at least 4 (\pm 2) hours after dosing, at response, and at the EOT.
- ^q For subjects who discontinued study treatment without confirmed disease progression or start of subsequent anticancer treatment, tumor assessments will continue during LTFU every 12 weeks (\pm 2 weeks) for up to 3 years after last subject enrolled or until confirmed disease progression, start of subsequent anticancer treatment, death, withdrawal of consent, loss to follow-up, or end of study.

Approved

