AMG 510-related changes in the rat were minimal to mild and included kidney tubular epithelial degeneration/necrosis; increased spleen weight, increased leukocytes; and a decrease in red blood cell (RBC) mass (hemoglobin, RBC count, and hematocrit) that was associated with changes in reticulocytes and RBC indices. In the rat, AMG 510-related degeneration/necrosis of renal tubule epithelium primarily affected tubules within the outer segment of the outer medulla and was characterized by sloughing of degenerative/necrotic epithelial cells, tubular dilatation, and/or accumulation of eosinophilic material within the tubule. Reversibility data is pending in the rat. The degeneration/necrosis observed in the kidney is expected to be fully reversible based on the minimal to mild severity, the absence of tubular basement membrane damage, and the normal regenerative capacity of the renal tubular epithelium. Key AMG 510-related changes in the dog consisted of a minimal to mild decrease in RBC mass associated with decreased reticulocytes. Taken together, the AMG 510-related decrease in RBC mass and reticulocytes in the rat and dog are most likely due to red blood cell/reticulocyte destruction and not decreased hematopoietic production, given the absence of light microscopic changes in the bone marrow in dog and the increased bone marrow erythroid cellularity in a few rats. The decreases in RBC mass and reticulocytes are expected to be reversible based on the normal regenerative capacity of the hematopoietic system, and the absence of overt bone marrow toxicity (eg, hypocellularity). AMG 510 nonclinical safety studies have not identified cardiovascular concerns. Clinically significant interaction with the hERG channel are not expected over the proposed clinical dose range (hERG IC₅₀ 54.8 µM). AMG 510 at doses up to 300 mg/kg did not result in changes to electrocardiogram (ECG) or hemodynamic parameters in a cardiovascular safety pharmacology study in telemetered dogs or in a 28-day toxicology study. In exploratory genetic toxicology studies, AMG 510 was not mutagenic in the Ames bacterial mutagenicity assay but was positive for clastogenicity in vitro. AMG 510 was not phototoxic in vitro.

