2.5 Risk Assessment

There are no identified risks associated with the administration of AMG 510. Based on nonclinical toxicity studies of AMG 510, **key safety information for AMG 510** includes renal toxicity, anemia, leukocytosis, and splenomegaly. Clinical signs and symptoms of **this key safety information**, along with safety laboratories, will be monitored during the study to ensure subjects' safety.

More detailed information about the risks of AMG 510 may be found in the [AMG 510 Investigator's Brochure](#).

Approved

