Tumor biopsy (optional, as applicable) or archived tumor tissue (FFPE) for solid tumors		X ^o																				X ^p	

Footnotes defined on last page of [Table 6](#).

Approved

Table 6. Schedule of Assessment: Phase 2 Study Visits Through Cycle 2 Treatment and LTFU

	Treatment											EOT	SFU	LTFU		
Cycle	2						8	3,5 ^a			4,6	QC	Q2C			
Day	1						8	1			1	1	1			
Hours (relative to dosing)	pre	0	0.25	0.5	1	4		pre	1	4						
GENERAL & SAFETY																
Physical exam & weight	X							X			X	X			X	
ECOG	X							X			X	X		X	X	
Vital signs	X															
ECG (Group A) ^{b, c}	X				X	X			X		X	X			X	
ECG (Group B) ^{b, c}															X	
Anticancer therapy															X	X
Concomitant medications	←-----→															
Adverse events	←-----→															
Serious adverse events	←-----→															
Patient diaries	←-----→															

Footnotes defined on last page of the table.

Approved

Table 6. Schedule of Assessment: Phase 2 Study Visits Through Cycle 2 Treatment and LTFU

	Treatment												EOT	SFU	LTFU	
Cycle	2						8	3,5			4,6	QC	Q2C			
Day	1						8	1			1	1	1			
Hours (relative to dosing)	pre	0	0.25	0.5	1	4		pre	1	4						
Patient-reported Outcomes																
EORTC QLQ C30	X							X			X		X	X	X	
QLQ LC13	X							X			X		X	X	X	
NSCLC SAQ	X							X			X		X	X	X	
QLQ PAN26	X							X			X		X	X	X	
PRO-CTCAE	X							X			X		X	X	X	
EQ-5D-5L	X							X			X		X	X	X	
GP5 of the FACT-G	X							X			X		X	X	X	
Laboratory^d																
Chemistry	X							X			X	X				
Hematology	X							X			X	X				
Coagulation	X							X			X	X				
Urinalysis ^e	X							X			X	X				
Serum pregnancy test ^f															X	
Urine pregnancy test^f	X							X			X	X				

Approved

Footnotes defined on last page of the table.

Table 6. Schedule of Assessment: Phase 2 Study Visits Through Cycle 2 Treatment and LTFU

	Treatment													EOT	SFU	LTFU
Cycle	2							3,5			4,6	QC	Q2C			
Day	1						8	1		1	1	1				
Hours (relative to dosing)	pre	0	0.25	0.5	1	4		pre	1	4						
DOSING																
AMG 510 ^g	←-----→															
IMAGING ASSESSMENTS																
Radiological imaging, (CT/MRI) and tumor assessment ^h								X						X	X	(X) ^a
MRI brain ⁱ																
PK ASSESSMENTS																
AMG 510 PK (Group A) ⁱ	X				X	X		X	X	X				X		
AMG 510 PK (Group B) ⁱ	X				X	X		X	X	X				X		
BIOMARKER SAMPLES																
Tumor markers at site ^k	(X)															
Plasma ctDNA ^l	X							X			X	X		X		
Cell pellet from plasma ^m																

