Footnotes defined on last page of the table.

Approved

Table 6. Schedule of Assessment: Phase 2 Study Visits Through Cycle 2 Treatment and LTFU

	Treatment												EOT	SFU	LTFU
Cycle	2						3,5		4,6	QC	Q2C				
Day	1						1		1	1	1				
Hours (relative to dosing)	pre	0	0.25	0.5	1	4		pre	1	4					
BIOMARKER SAMPLES Cont.															
Serum	X							X			X	X		X	
PB Paxgene RNA	X							X			X	X		X	
Stool sample ⁿ														X	
BIOMARKER DEVELOPMENT															
Tumor biopsy (optional, as applicable)	(X) ^P												X ^P		

Footnotes defined on next page

Approved

CNS = central nervous system; CT = computed tomography; cfDNA = cell-free DNA; ECG = electrocardiogram; ECOG = Eastern Cooperative Oncology Group; EOT = end of treatment; FFPE = formalin-fixed paraffin-embedded; HbA1c = hemoglobin A1c; LTFU = long-term follow-up; MRI = magnetic resonance imaging; NSCLC = non-small cell lung carcinoma; PD-L1 = programmed cell death-1; PET = positron emission tomography; **PB = peripheral blood**; PK = pharmacokinetic; PRO-CTCAE = Patient-Reported Outcomes version of the Common Terminology Criteria for Adverse Events; QC = every cycle from cycle 7 and beyond (cycles 7, 8, 9, etc), Q2C = every other cycle from cycle 7 and beyond (cycles 7, 9, 11 etc); SFU = safety follow-up.

(X) = Parentheses indicate that the particular test is situational at that time point, as specified in the respective notes.

^a **KRAS p.G12C testing results must be available** prior to starting all other screening procedures

^b **Three triplicate ECGs must be performed at screening. For all other visits, one triplicate ECG must be performed. Each tracing must be at least 30 seconds apart.**

^c Intense ECG collection will be performed in up to approximately 30 subjects at time points described for Group A. Sparse ECG collection will be performed in the remaining subjects at time points described for Group B.

^d Assessments to be performed on day 1 of each cycle. Laboratory assessments may be performed within 24 hours before day 1 of each cycle. A window of ± 1 day is allowable for cycle 1 and cycle 2. A window of ± 2 days is allowable after cycle 2. Electrocardiograms, biomarker blood draws, safety labs, vital signs (including pulse oximetry): ± 5 minute window (for time points of 0.25 hour and 0.5 hour postdose), ± 15 -minute window (all other time points).

^e Microscopic exam required to be performed with each time point collected.

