7.2.3 End-of-treatment Visit

For subjects who discontinue investigational product, the EOT visit should occur as soon as possible (within 14 days) after the last dose of investigational product.

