7.2.4 Safety Follow-up Visit

The SFU visit should occur approximately 30 (+7) days after the last dose of AMG 510 or before any new anticancer treatment is started.

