7.4 Clinical Laboratory Assessments

Refer to [Table 7](#) for the list of analytes to be performed and to the Schedule of Assessments ([Table 2](#), [Table 5](#), and [Table 6](#)) for the timing and frequency.

The investigator is responsible for reviewing laboratory test results and recording any clinically relevant changes occurring during the study in the Event CRF. The investigator must determine whether an abnormal value in an individual study subject represents a clinically significant change from the subject's baseline values. In general, abnormal laboratory findings without clinical significance (based on the investigator's judgment) are not to be recorded as adverse events. However, laboratory value changes that require treatment or adjustment in current therapy are considered adverse events. Where applicable, clinical sequelae (not the laboratory abnormality) are to be recorded as the adverse event.

All protocol-required laboratory assessments, as defined in [Table 7](#), must be conducted in accordance with the laboratory manual and the Schedule of Assessments ([Table 2](#), [Table 5](#), and [Table 6](#)).

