9.6.3 Laboratory Test Results

Laboratory data will be summarized using standard descriptive statistics at each scheduled time point in the study. For continuous parameters, a summary of the changes from baseline to each post dose laboratory assessment will also be produced. Shifts in selected laboratory parameters between baseline and the worst on-study value will be summarized according to the NCI CTCAE toxicity grades. Safety Laboratory collection includes chemistry, hematology, pregnancy test (for women of child-bearing potential) either urine or serum, and urine albumin-creatinine ratio

The parameters described in [Table 7](#) of the protocol will be collected, converted to Amgen standard units and summarized.

Selected individual analytes will be summarized by cohort using standard descriptive statistics at each of the scheduled time points through the study up to the safety follow-up visit. For continuous parameters, a summary of the changes from baseline to each post-dose laboratory assessment will be produced for each cohort.

Tables of shifts from baseline to the worst-case on-study increased and decreased values (graded according to the NCI Common Toxicity Grading Criteria) will be provided for selected laboratory parameters with available NCI-CTCAE grades. Unscheduled assessments will be included in the shift tables.

Subject incidence of suspected Hy's law cases (Hy's law predicts potential for drug-related hepatotoxicity) will be summarized by cohort. A listing of alanine aminotransferase, aspartate aminotransferase, alkaline phosphatase, and total bilirubin values at each time point will be produced for the subjects suspected of Hy's law case.

Boxplots may be plotted by time point and cohort for selected analytes.

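### Phase 2 schedules no safety laboratory panel at end of treatment or safety follow-up, so about 30 to 50 days up to the close of the adverse-event window have no planned draw

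*Supplement*

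**What the plan says.** The phase 2 schedule after cycle 1 is in protocol Section 7.1, "Table 6. Schedule of Assessment: Phase 2 Study Visits Through Cycle 2 Treatment and LTFU". Its chemistry, hematology, coagulation and urinalysis rows are identical: marked at cycle 2 day 1, cycles 3 and 5, cycles 4 and 6, and every cycle from 7, and blank at EOT and SFU. Footnote d, attached to the laboratory block, reads "Assessments to be performed on day 1 of each cycle. Laboratory assessments may be performed within 24 hours before day 1 of each cycle" and then gives visit windows.

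No other section adds tests at those two visits. Section 7.4 says protocol-required laboratory assessments "must be conducted in accordance with the laboratory manual and the Schedule of Assessments". Sections 7.2.3 and 7.2.4 set timing only: "the EOT visit should occur as soon as possible (within 14 days) after the last dose of investigational product", and "The SFU visit should occur approximately 30 (+7) days after the last dose of AMG 510" or before new anticancer treatment starts.

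On the safety side, Section 2.5 says the key safety information from nonclinical work "includes renal toxicity, anemia, leukocytosis, and splenomegaly" and that safety laboratories will be among the means of monitoring. Section 2.3.3 expects the kidney and red-cell findings to reverse, but notes "Reversibility data is pending in the rat". Section 9.2.1.1 collects adverse events through the SFU visit. SAP Section 5 counts treatment-emergent events to 30 days after the last dose (or end of study, if earlier). SAP 9.6.3 summarizes selected analytes "at each of the scheduled time points through the study up to the safety follow-up visit".

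**The concern.** Renal toxicity, anemia and leukocytosis, three of the four risks named in Section 2.5, are found mainly by laboratory test. Section 7.4 has the investigator record clinically relevant laboratory changes as events, so an abnormality without symptoms becomes an adverse event only if someone draws blood or urine. The schedule stops drawing at the start of the last cycle, while the adverse-event window runs on through the rest of that cycle and 30 days beyond.

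Two things are at stake. One is ascertainment: incidence and severity of adverse events is a phase 2 secondary endpoint, and the final stretch of its window has no systematic laboratory measurement. The other is recovery: the protocol expects the kidney and red-cell effects to reverse, and post-treatment panels would give uniform data on whether they do in patients.

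**Working it through.** **1. Is the blank real?** The text available here was read from a PDF and some table columns have shifted, so the reading needs support beyond column position.

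- Other rows of the same table do reach these visits: ECOG and the patient-reported outcomes at EOT and SFU; PK and ctDNA blood at EOT; physical exam, ECG and the serum pregnancy test at SFU. The columns were not cut off.
- Each of the four laboratory rows has four marks. The ctDNA row has those four plus a fifth at EOT; the physical exam row has those four plus a fifth at SFU.
- The urine pregnancy test row has the same four marks, and the protocol's Summary of Changes describes that test as added on day 1 of every cycle. The four-mark pattern is therefore the every-cycle pattern, with no mark left over for EOT or SFU.

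**2. Inputs for the gap**

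- Last scheduled draw from cycle 2 on: day 1 of the cycle (Table 6).
- Cycle length: 21 days. This is stated for phase 1 in Section 2.6.1.1 and assumed here for phase 2.
- End of the treatment-emergent window: last dose + 30 days (SAP Section 5).

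Gap = (cycle day of last dose − cycle day of last scheduled draw) + 30.

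| Last dose, cycle 2 or later | Gap to end of window |
|---|---|
| Cycle day 1 | (1 − 1) + 30 = 30 days |
| Cycle day 11 | (11 − 1) + 30 = 40 days |
| Cycle day 21 | (21 − 1) + 30 = 50 days |

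The draw and visit windows in footnote d move these figures by 1 to 2 days. For a subject who stops during cycle 1 the gap is shorter, because Table 5 also has panels on days 8 and 15: at most (21 − 15) + 30 = 36 days. If the end point is instead an SFU visit at its latest, last dose + 37, the range for cycle 2 or later is 37 to 57 days. That runs past the treatment-emergent window, so it is not used as the size of this point.

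**3. Schedule against analysis plan**

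| Item | Runs to | Scheduled panel there? |
|---|---|---|
| Adverse-event collection (9.2.1.1) | SFU | No |
| Treatment-emergent window (SAP 5) | Last dose + 30 days | No |
| Laboratory summaries (SAP 9.6.3) | Scheduled time points up to SFU | None after day 1 of the last cycle |

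**4. With panels added.** EOT falls within 14 days of the last dose, so the longest wait from the last cycle's day 1 to the EOT panel would be (21 − 1) + 14 = 34 days. A panel at an SFU visit held on or after day 30 would close the window with a measurement.

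**The case against.** The strongest reply is that the absence of a scheduled test is not the absence of testing. Much of it stands.

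- Section 7.2 allows standard-of-care procedures at the investigator's discretion.
- Adverse events are followed until they stabilize or reverse (9.2.1.1). Listed toxicities prompt repeat hematology within 3 days (6.1.1.3). Potential liver injury brings at least 4 weeks of close observation after discontinuation (Appendix F).
- SAP 9.6.3 admits unscheduled results to the shift tables, so those tables are not blind to late values.

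A reader might therefore infer too much: that these risks are never measured late, that recovery could not be described at all, or that the shift tables must understate late toxicity. The documents support none of these as absolutes. The triggered tests, however, act on abnormalities already noticed, and discretionary tests are not uniform across subjects. Neither reliably finds a new silent change.

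A reader might also take footnote d as proof that laboratory tests are confined to day 1. It is not. The same footnote heads the Table 5 block, with marks at screening and on days 8 and 15, and the Table 6 block, where the serum pregnancy test is marked at SFU. It sets timing and windows and excludes nothing; the evidence is the rows themselves. Likewise, the SAP's limit at safety follow-up says which scheduled points are summarized. It does not itself order a draw there, so the mismatch suggests an oversight without proving one.

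Finally, the Table 6 vital signs row shows one mark, at cycle 2 day 1, which might be read as vital signs stopping for the rest of treatment. That rests on a single row of a table whose columns have shifted elsewhere: the Table 5 biopsy mark, for example, falls under day 15 although footnote p puts it on day 8. Vital signs also do not measure the renal or blood risks. It is a separate query, held with lower confidence.

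**Conclusion.** The laboratory point holds in a limited form. Phase 2 has no scheduled chemistry, hematology, coagulation or urinalysis at EOT or SFU. For subjects who reach cycle 2, the last scheduled panel precedes the end of the treatment-emergent window by about 30 to 50 days, depending on when in the cycle dosing stops. This assumes 21-day cycles, and the stretch is shorter if SFU is brought forward for new anticancer treatment. The schedule applies to all of the approximately 200 planned phase 2 subjects, but that is total enrollment and not the number who would have the longest gap.

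The consequence is incomplete ascertainment of new silent laboratory abnormalities, and no uniform data on recovery after stopping. The primary response analysis is unaffected. This is an inexpensive improvement to safety data collection that the sponsor should make. The vital signs row needs checking against the source document before anything is concluded from it.

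**What to change.** - In Table 6, mark chemistry, hematology, coagulation and urinalysis (with the microscopic exam that footnote e already requires) at EOT and SFU.
- Extend footnote d to cover those two visits.
- SAP 9.6.3 can stay as it is, since its summaries already run to the safety follow-up visit.
- Separately, check the Table 6 vital signs row against the source document. If the single mark is correct, mark vital signs at the later visits where a physical exam is already done (day 1 of cycles 3 onward, and SFU), so that SAP 9.6.4 has scheduled data to summarize.

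The cost is a schedule amendment and local laboratory panels at two visits that already take place. Blood is already drawn at EOT for PK and biomarkers, and SFU already includes an examination and an ECG. The change concerns data collection only and touches no dosing or stopping rule.

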7.2 General Study Procedures

Study procedures and their time points are summarized in the Schedule of Assessments (see Table 2 through Table 6). Refer to the IPIM, laboratory and site imaging manuals for detailed collection and handling procedures.

Adherence to the study design requirements, including those specified in the Schedule of Assessments, is essential and required for study conduct.

A signed and dated IRB/IEC approved ICF must be obtained prior to performing any study specific procedures, including discontinuing standard therapy for observing study specific washout periods.

Subjects will be seen in the clinic for study evaluations. **During all visits invasive procedures like blood draws or biopsies should be completed after ECGs, vital signs, and COAs (as applicable).**

Blood samples for biomarker and PK assessments should be drawn from a peripheral vein and not from a central venous catheter. The study specific lab manual will provide additional detail on lab sampling and handling requirements.

Study procedures should be performed and samples obtained at the time points stipulated in the Schedules of Assessments (Table 2, Table 3, Table 4, Table 5, and Table 6). Acceptable deviation windows for study procedures are listed below:

- ECGs, biomarker blood draws, safety labs, vital signs (including pulse oximetry):
± 5 minute window (for time points of 0.25 hr and 0.5 hr postdose), ± 15 minute window (all other time points)

Acceptable deviation windows for study visits are listed below:

- visits during treatment: ± 1 day for cycle 1 and cycle 2
- visits during treatment: ± 2 days after cycle 2
- SFU: + 7 days
- LTFU: ± 2 weeks

Furthermore, start of a treatment can be delayed for administrative/logistical reasons for up to 7 days to allow for appropriate scheduling after discussion with and final approval by sponsor.

Any missed visits, tests not done, or examinations that are not conducted must be reported as such on the eCRFs. Subsequent study visits should resume on the original schedule. Missed assessments at prior visits should not be duplicated at subsequent

visits. Every effort should be taken to collect all biomarker and PK samples as described in the schedule of assessments. However, if sample processing/shipment on a weekend/holiday is not logistically feasible for a site, this needs to be documented and will not be considered a deviation from the protocol.

Additional procedures deemed necessary as part of standard of care or as required by local laws and regulations may be performed at the Investigator's discretion.

Table 7. List of Analytes

Local Laboratory			Central Laboratory
Chemistry	Hematology	Coagulation	PK and Biomarker
Sodium	Hemoglobin	PT or INR	PK sampling
Potassium	Hematocrit	aPTT Fibrinogen	Plasma ctDNA
Chloride	Mean corpuscular volume	D-Dimer	Plasma cell pellet
Bicarbonate Total protein	Platelets		Serum
Albumin	RBC		PB Paxgene RNA
Calcium	White blood cell Differential		Antibody
Magnesium	• Total neutrophils		Tumor biopsy ^c
Phosphorous	• Eosinophils		
Glucose	• Basophils		
Blood urea nitrogen	• Lymphocytes		
Urea ^a	Monocytes		
Creatinine			
Total creatine kinase	Serology ^b	Urinalysis	
Total bilirubin	HepBsAg	Specific gravity, pH,	
Direct bilirubin	HepCAb	Blood protein,	
Serum or Urine	HIV	glucose, bilirubin,	
Pregnancy		WBC, ketones,	
Alkaline phosphatase	Tumor markers	sodium, potassium	
Alanine aminotransferase	-Carcinoembryonic embryonic antigen (CEA)	RBC, epithelial cells, bacteria	
Aspartate aminotransferase	-Carbohydrate antigen (CA 19-9)	Microscopic exam:	
HbA1c	-Cancer antigen (CA 125)	• Cellular casts	
		• Granular casts	
		• Hemoglobin casts	
		• Hyaline casts	
		• Mixed casts	

Footnotes defined on next page of this table

Approved

HbA1c = hemoglobin A1c; HepBsAg = hepatitis B surface antigen; HepCAb = hepatitis C antibody; INR = international normalized ratio; LDH = lactate dehydrogenase; PB = peripheral blood; PK = pharmacokinetics; PT = prothrombin time; PTT = partial thromboplastin time; RBC = red blood cell count; WBC = white blood cell count.

^a Urea collection is acceptable in absence of BUN.

^b Hepatitis B surface antigen, hepatitis C antibody, PCR for Hepatitis C RNA (if Hepatitis C antibody is positive), and HIV assessments.

^c Archived tumor tissue is acceptable. If archived tumor tissues is not available, a tumor biopsy should be performed prior to treatment.

